### **Risks**

Hot flashes (flushing), dizziness, headache, increased sweating, decreased libido, trouble sleeping, nausea, change in breast size, hair loss, or mental/mood changes (such as depression, mood swings, hallucinations) may occur. Pain, bruising, bleeding, redness, or swelling at the injection site may also occur. In women, vaginal dryness may also occur.

## 10.4. Drug Name

Lupron® (leuprolide acetate)

### Classification

Luteinizing hormone releasing hormone (LHRH) agonist

### **Mechanism of Action**

Leuprolide acetate is a synthetic nonapeptide analogue of GnRH. Leuprolide acetate is a long-acting GnRH analog. A single monthly injection of LUPRON DEPOT 3.75 mg results in an initial stimulation followed by a prolonged suppression of pituitary gonadotropins.

## **How Supplied**

Each syringe contains sterile lyophilized microspheres, which is leuprolide incorporated in a biodegradable copolymer of lactic and glycolic acids.

### **Availability**

Commercial supplies of leuprolide will be used in this study and billed to third party payers or the subject.

## Storage, Handling, and Accountability

Store at 25°C (77°F); excursions permitted to 15-30°C (59-86°F)

### Administration

Leuprolide, at a dose of 3.75 mg, should be administered intramuscularly on day 1 of each cycle into the gluteal area, anterior thigh, or deltoid; injection sites should be alternated. using an aseptic technique by qualified medical personnel.

#### **Risks**

Estradiol levels may increase during the first weeks following the initial injection of leuprolide, but then decline to menopausal levels. This transient increase in estradiol can be associated with a temporary worsening of signs and symptoms.

As would be expected with a drug that lowers serum estradiol levels, the most frequently reported adverse reactions were those related to hypoestrogenism. Adverse events occurring in clinical studies with LUPRON DEPOT that are associated with hypoestrogenism include: hot flashes, headaches, emotional lability, decreased libido, acne, myalgia, reduction in breast size, and vaginal dryness. Patients should be counseled on the possibility of the development or worsening of depression and the occurrence of memory disorders.

The induced hypoestrogenic state also results in a loss in bone density over the course of treatment, some of which may not be reversible.

Pain, bruising, bleeding, redness, or swelling at the injection site may also occur.

#### 11. ADVERSE EVENTS

#### 11.1. Definitions of Adverse Events

## 11.1.1. Adverse Event (AE):

An AE is any unfavorable and unintended medical occurrence during the course of the study whether or not considered related to the study therapy. The following are examples of AEs:

- A sign (including an abnormal laboratory finding) or symptom
- A disease temporally associated with participation in an investigational study
- An intercurrent illness or injury that impairs the well-being of the subject

Hospitalization for elective surgery or routine clinical procedures that are not the result of an AE (e.g., surgical insertion of central line) should not be recorded as an AE. Disease progression should not be recorded as an AE, unless it is attributable by the site investigator to the study therapy.

## 11.1.2. Serious Adverse Event (SAE):

A SAE is an adverse event that:

- Results in death. NOTE: Death due to disease progression should not be reported as a SAE, unless it is attributable by the site investigator to the study drug(s)
- Is life-threatening (defined as an event in which the subject was at risk of death at the time of the event; it does not refer to an event which hypothetically might have caused death if it were more severe)
- Requires inpatient hospitalization for >24 hours or prolongation of existing
  hospitalization. NOTE: Hospitalization for anticipated or protocol specified
  procedures such as administration of chemotherapy, central line insertion, metastasis
  interventional therapy, resection of primary tumor, or elective surgery, will not be
  considered serious adverse events.
- Results in persistent or significant disability/incapacity
- Is a congenital anomaly or birth defect
- Is an important medical event (defined as a medical event(s) that may not be immediately life-threatening or result in death or hospitalization but, based upon appropriate medical and scientific judgment, may jeopardize the subject or may require intervention (e.g., medical, surgical) to prevent one of the other serious outcomes listed in the definition above). Examples of such events include, but are not limited to, intensive treatment in an emergency room or at home for allergic bronchospasm; blood dyscrasias or convulsions not resulting in hospitalization; or the development of drug dependency or drug abuse.
  - Palbociclib overdose. For purposes of this trial, an overdose will be defined as any
    dose exceeding the prescribed dose for palbociclib by 20% over the prescribed
    dose.

## 11.1.3. Unexpected Adverse Event:

For this study, an AE is considered unexpected when it varies in nature, intensity or frequency from information provided in the current Investigator's Brochure (IB),

prescribing information or when it is not included in the informed consent document as a potential risk. Unexpected also refers to AEs that are mentioned in the IB as occurring with a class of drugs or are anticipated from the pharmacological properties of the drug, but are not specifically mentioned as occurring with the particular drug under investigation.

### 11.1.4. Causality

AEs will be categorized according to the likelihood that they are related to the study drug(s). Specifically, they will be categorized using the following terms:

Unrelated	The Adverse Event is clearly not related to the drug(s)
Unlikely	The Adverse Event is doubtfully related to the drug(s)
Possible	The Adverse Event may be related to the drug(s)
Probable	The Adverse Event is likely related to the drug(s)
Definite	The Adverse Event is clearly related to the drug(s)

## 11.2. Adverse Event (AE) Reporting

- Adverse events (AEs) will be recorded from the time of consent and for at least 30 days after last dose of study drug.
- AEs will be recorded regardless of whether or not the event(s) are considered related to trial medications.
- All AEs considered related to trial medication will be followed until resolution, return to baseline or ≤ Grade 1, deemed clinically insignificant, and/or until a new anti-cancer treatment starts, whichever is earlier

## 11.3. Reporting of Pregnancy

Although pregnancy is not considered an adverse event, it is the responsibility of investigators or their designees to report any pregnancy in a subject (spontaneously reported to them) that occurs during the trial or within 120 days of last dose of study drug. All subjects who become pregnant must be followed to the completion/termination of the pregnancy. All pregnancies must be reported within 1 business day to BTCRC AHQ on the Pregnancy Report form (See Documents/Info tab of the EDC).

Pregnancy outcomes of spontaneous abortion, missed abortion, benign hydatidiform mole, blighted ovum, fetal death, intrauterine death, miscarriage, and stillbirth must be reported as serious events (Important Medical Events). If the pregnancy continues to term, the outcome (health of infant) must also be reported. Such events must be reported within 1 business day to BTCRC AHQ. BTCRC AHQ will report the event within 1 business day to Pfizer Global Safety (Attn: Worldwide Product Safety; [contact]).

## 11.4. Serious Adverse Event (SAE) Reporting

## 11.4.1. Study Center (Site) Requirements for Reporting SAEs:

• SAEs caused by a protocol-mandated intervention occurring after informed consent but prior to initiation of study therapy will be recorded (e.g. SAEs related to invasive procedures such as biopsies or medication washout).

- SAEs that occur on or after initiation of study therapy until 90 days after last dose of study therapy or until a new anti-cancer treatment starts, whichever occurs first, will be reported within 1 business day of discovery of the event.
- SAEs include events related and unrelated to the study therapy.
- All SAEs regardless of relation to study drug will be followed until resolution to ≤ Grade 1 or baseline and/or deemed clinically insignificant and/or until a new anticancer treatment starts, whichever occurs first.
- For any pregnancy SAE, the site investigator will follow the female subject until completion of the pregnancy, and must document the outcome of the pregnancy (either normal or abnormal outcome). If the outcome of the pregnancy was abnormal (e.g., spontaneous or therapeutic abortion), the site investigator should report the abnormal outcome as an AE. If the abnormal outcome meets any of the serious criteria, it must be reported as an SAE. This information will be reported on the Pregnancy Form.

The completed SAE Submission Form (see Documents/Info tab of the EDC) must be sent to Big Ten Cancer Research Consortium (BTCRC) Administrative Headquarters (AHQ) within 1 business day of discovery of the event. The form must be sent electronically to [contact]. The site investigator is responsible for informing the IRB and/or other local regulatory bodies of the SAE as per local requirements.

The original copy of the SAE Submission Form and the e-mail correspondence must be kept within the study file at the study site.

Once the SAE has resolved (see resolution guidelines listed in 11.2.2.1), sites must submit a follow up SAE Submission Form within a reasonable timeframe to BTCRC AHQ at [contact].

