#### 6. DOSE DELAYS

The NCI Common Terminology Criteria for Adverse Events (CTCAE) Version 4 will be used to grade adverse events.

Subjects enrolled in this study will be evaluated clinically and with standard laboratory tests before and at regular intervals during their participation in this study as specified in Section 7.

Subjects will be evaluated for adverse events (all grades), serious adverse events, and adverse events requiring protocol therapy interruption or discontinuation at each study visit for the duration of their participation in the study.

Subjects discontinued from the study drug for any reason will be evaluated within 30 days ( $\pm$  7) of the last dose of study drug.

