#### Footnotes:

- 1: For cycle 1 only: labs do not need to be repeated if done within 7 days of day 1.
- 2: Blood Chemistries to include: sodium, potassium, serum creatinine (or GFR; see 3.1.8), calcium, albumin, ALT, AST, bilirubin, alkaline phosphatase.
- 3: For Cycles 1 and 2 only, hematology assessments done on Day 1 and also on Day 15
- 4: A negative serum or urine pregnancy test is required within 72 hours of study registration and at the beginning of each cycle, if clinically indicated. If the urine test cannot be confirmed as negative, a serum pregnancy test will be required.
- 5: For subjects with unresolved treatment-related toxicity, follow as medically appropriate until resolution or stabilization
- 6: Survival assessment to be recorded every 3 months until 2 years from registration
- 7: Appropriate scans to assess disease status will be obtained within 28 days of study enrollment including CT chest, abdomen/pelvis. PET/CT: The CT portion of PET/CT is usually of lower quality and should typically not be used in place of dedicated diagnostic CT. However, if the CT portion is of diagnostic quality, it may be used.
- 8: Disease assessment will be performed on Day 1 of every 2 cycles starting at cycle 3 (ex. Day 1 of cycle 3, 5, 7, etc.) for the first 19 cycles (18 months). Disease assessment will be performed on Day 1 of every three cycles starting at cycle 22 (ex. Day 1 of cycle 22, 25, etc.) until discontinuation of study drug.
- 9: Bone scan will be repeated as per footnote 8 above only if positive for bone mets at the time of screening or if clinically indicated.
- 10: If bone lesion(s) detected from whole body bone scan, perform bone x-ray, CT or MRI of the largest bone metastatic area.
- 11: Histological confirmation of breast cancer diagnosis is required (Section 3.1.3). Although not required as a protocol procedure, a patient with a new metastatic lesion should be considered for biopsy whenever possible to reassess ER/PR/HER2 status, if clinically indicated. Also, biopsy at the time of progression should be considered as clinically indicated, but it is not required as a protocol procedure. If a biopsy is prospectively done as standard of care, the study would like to collect samples for correlative research. Unstained slides from either the fresh biopsy or from an archival tumor specimen (metastatic lesion) may be submitted at baseline.

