## 7.6. Safety Follow-up Evaluations

Subjects discontinued from the treatment phase of the study for any reason will be evaluated within 30 days ( $\pm$  7) of the last dose of study drug.

- Physical exam, weight
- Vital signs
- ECOG performance status
- Assess adverse events
- Concomitant medications
- Correlative blood samples at the time of progression
- Optional standard biopsy at the time of progression, with extra passes for research.
- Banking samples. See Correlative Laboratory Manual for specific instructions.

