# 7.7. Long Term Follow-up Evaluations (±14 days)

Subjects will continue to be followed for survival every 3 months for 24 months after registration.

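### SAEs are reportable to 90 days after last dose, but no scheduled contact after the day-30 safety visit asks about them, so they may be under-ascertained

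*Combined protocol and SAP*

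**What the plan says.** **SAE window.** Section 11.4.1 covers related and unrelated SAEs from the start of study therapy "until 90 days after last dose of study therapy or until a new anti-cancer treatment starts, whichever occurs first". The trigger is discovery, not a visit: such events "will be reported within 1 business day of discovery of the event".

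**AE window.** Section 11.2 states: "Adverse events (AEs) will be recorded from the time of consent and for at least 30 days after last dose of study drug". It also states: "AEs will be recorded regardless of whether or not the event(s) are considered related to trial medications". Recording has no cut-off at new therapy. Only the follow-up of related AEs may stop there.

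**Scheduled assessments.** Section 7.6 states: "Subjects discontinued from the treatment phase of the study for any reason will be evaluated within 30 days" (±7). This is the last calendar column with an AE mark. The long-term column in Section 7 marks survival and CT/MRI only, and footnote 6 and Section 7.7 describe survival only.

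**Length of long-term follow-up.** Section 7.7 states: "Subjects will continue to be followed for survival every 3 months for 24 months after registration". The calendar and footnote 6 agree with it. Sections 5.1 and 7.5.1 instead count 24 months from discontinuation.

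**Unresolved toxicity.** Calendar footnote 5 states: "For subjects with unresolved treatment-related toxicity, follow as medically appropriate until resolution or stabilization". Section 11.2 gives several possible end points for related AEs, one of which is the start of new anti-cancer treatment.

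**The concern.** The reporting window is three times as long as the period covered by a scheduled safety assessment. After the safety visit the plan relies on the site happening to learn of an SAE, although it has set itself a 90-day window for such events. Safety and tolerability is the first-listed secondary objective (Section 2.1.2), and Section 10.2 lists blood clots and stroke among the serious tamoxifen risks. Incomplete capture after day 30 would understate late toxicity.

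Two other rules add to the uncertainty. The conflicting end of survival follow-up leaves open whether a subject who stops drug after a long time on treatment is contacted at all between the safety visit and day 90. And the SAE window can close before the AE window in a subject who moves quickly to a new treatment.

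**Working it through.** The plan gives no figure for this point, so there is none to reproduce. The check sets the windows side by side.

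**1. Days without a scheduled AE or SAE question**

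Inputs: SAE window of 90 days (11.4.1); safety visit at day 30 ±7, so day 23 to day 37 (calendar, 7.6). Uncovered days = 90 − visit day.

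- Visit on day 23: 90 − 23 = 67 days; 67/90 = 74%.
- Visit on day 30: 90 − 30 = 60 days; 60/90 = 67%.
- Visit on day 37: 90 − 37 = 53 days; 53/90 = 59%.

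These are maxima. They apply to a subject who starts no new therapy. If new treatment starts after the safety visit but before day 90, the window closes then and the uncovered stretch is shorter. If it starts before the visit, no uncovered stretch remains.

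**2. Long-treated subjects, under each reading of the follow-up anchor**

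Inputs: planning medians for PFS of 15 months (null) and 25 months (alternative), the exponential assumption, and N = 48 (Section 12.3). Further assumption: subjects stay on drug until a PFS event. Then P(on drug beyond 24 months) = 0.5^(24/median).

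- Median 15 months: 0.5^(24/15) = 0.33; 48 × 0.33 ≈ 16 subjects.
- Median 25 months: 0.5^(24/25) = 0.51; 48 × 0.514 ≈ 25 subjects.

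On the registration reading (calendar, footnote 6, 7.7), survival contacts have ended for these subjects before they stop drug, so nothing is scheduled after the safety visit. On the discontinuation reading (5.1, 7.5.1), contacts continue and the share is zero, although the contacts still carry no SAE item. Section 7.5.1 also allows stopping for toxicity, physician decision or subject request, so fewer than 33% to 51% would still be on drug at those medians.

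**3. New therapy before day 30**

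If new anti-cancer treatment starts on day x < 30, SAE reporting closes on day x while AE recording runs to at least day 30. The overlap is 30 − x days. With x = 10 it is 20 days. A serious event on day 20 would be recorded under 11.2 but would carry no one-business-day duty under 11.4.1. It would then have no required route to the drug supplier (11.4.2) or to the sponsor-investigator's review of expectedness and relatedness (11.4.3). Section 5.5 prohibits no therapy in post-treatment follow-up, so an early switch is possible.

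**4. End of toxicity follow-up**

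For a subject with unresolved related toxicity who starts new treatment, footnote 5 continues to resolution or stabilization, whereas 11.2 permits stopping at new treatment. A site has no rule telling it which applies.

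**The case against.** A reader might infer that late serious events are simply missed. The documents do not support that. Reporting under 11.4.1 runs from discovery, so an SAE on day 60 is still reportable. Section 5.5 expects such events, since it asks for concomitant medications beyond 30 days to be recorded for SAEs. Section 6 says "Subjects will be evaluated for adverse events (all grades), serious adverse events" and applies this to every study visit while a subject takes part. Deaths are captured for as long as survival follow-up lasts.

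A reader might also infer that serious events after an early switch drop out of the data. They do not. They are recorded as AEs and can be picked up at the 30-day visit. Closing SAE reporting at new therapy is an explicit rule, and nothing in the documents requires all SAEs to day 30 to be reported regardless of new treatment.

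Finally, Section 12.5 tabulates AEs by CTCAE grade and specifies no SAE analysis and no 90-day window, so the effect on the planned table is limited.

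Most of this stands, and it limits the point to possible under-ascertainment. It does not remove the gap. The calendar puts no AE mark against long-term contacts, so the reach of Section 6 there is doubtful. A duty to report what is discovered is also not a schedule for asking. Where the protocol does mean to rely on volunteered information, for pregnancy in 11.3, it says so. Section 11.4.1 contains no such limit.

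**Conclusion.** The mismatch is real and modest. For a treated subject with no new therapy, about 60 of the 90 reportable days (53 to 67) have no scheduled AE or SAE question, and SAEs in that period may be under-ascertained. The documents give no SAE rate after treatment, so the number of events affected cannot be stated.

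It would go too far to say that 33% to 51% of subjects have no contact after the safety visit. That figure needs the registration reading, the planning medians with exponential PFS, and treatment until progression. On the discontinuation reading it is zero. What is established is that the two sets of passages conflict.

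The earlier closing of the SAE window is a separate issue about early events. It removes the expedited report, not the record. The difference over the end of toxicity follow-up is a minor wording matter. The primary PFS analysis is unaffected.

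**What to change.** Add an SAE question at a contact at or near day 90 after last dose, for treated subjects who have not started new anti-cancer therapy. It should cover the time since the safety visit. Use the survival contact where one falls then, and otherwise one telephone call. Mark the item in the calendar and in Section 7.7.

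Reconcile three sets of passages:

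- the end of long-term follow-up: Sections 5.1 and 7.5.1 with the calendar, footnote 6 and Section 7.7;
- the closing of AE recording and SAE reporting in the first 30 days: Section 11.2 with Section 11.4.1. Whichever rule is chosen, state how a serious event after an early switch is handled;
- the end of follow-up for related toxicity: footnote 5 with Section 11.2.

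The cost is a protocol wording change and at most one brief contact per subject. More subjects will need the separate call if the registration anchor is kept, because fewer survival contacts will then fall near day 90.

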### 11.4.2. BTCRC AHQ Requirements for Reporting SAEs to Pfizer:

BTCRC AHQ will submit all SAEs (e.g. SAEs, overdose, pregnancy, etc.) received from sites to Pfizer within one business day of receipt of the SAE Submission Form. BTCRC AHQ will provide follow-up information to Pfizer as it is received from participating site or within one business day.

BTCRC AHQ will fax SAE Submission Form for all SAE reports and any other relevant safety information to Pfizer Global Safety (Attn: Worldwide Product Safety) at:

# **[contact]

## 11.4.3. Sponsor-Investigator Responsibilities

BTCRC AHQ will send a SAE summary to the sponsor-investigator **within 1 business day** of receipt of SAE Submission Form from a site. The sponsor-investigator will promptly review the SAE summary and assess for expectedness and relatedness.

## 11.4.4. BTCRC AHQ Responsibilities to FDA

The FDA has concluded this protocol is exempt from the requirements of an IND. BTCRC AHQ will continue to facilitate compliance of applicable requirements for the sponsor-

investigator in relation to this study. This includes but is not limited to 21 CFR 50.20 informed consent, 21 CFR Part 56 IRB, and pertinent sections of the Public Health Service Act and FDAAA.

## **IND Safety Reports Unrelated to this Trial**

Pfizer will send IND safety reports from external studies that involve the study drug to BTCRC AHQ at ([contact]). BTCRC AHQ will forward safety reports to the sponsor-investigator who will review these reports and determine if revisions are needed to the protocol or consent. BTCRC AHQ will forward these reports to participating sites within 1 business day of receiving the sponsor-investigator's review. Based on the sponsor-investigator's review, applicable changes will be made to the protocol and informed consent document (if required). All IND safety reports will also be made available to sites via OnCore®.

Upon receipt from BTCRC AHQ, site investigators (or designees) are responsible for submitting these safety reports to their respective IRBs, as per their IRB policies.

